9.9.7 Data Removal

When participants withdraw consent from the study and ask for their data to be destroyed, their data will be marked as removed for future analyses in REDCap using standard REDCap functionality. The record, including its participant ID, will persist, as will records of ICFs that were signed, and the consent withdrawal record. All other data will be removed from REDCap. It will not be possible for participants to re-enroll once this data is removed.

Per the study protocols, data that are stored in the i2b2 Data Hub that have already been used for research will not be removed at the time of consent withdrawal.

When the study ends, all data will be de-identified in REDCap Central. The data in the i2b2 Data hub will persist in its existing de-identified form.

9.9.8 Data Integrity

Detailed Quality Control programs will be deployed to ensure and audit data integrity. The DRC team has extensive experience standing up and maintaining operational i2b2 instances (e.g., the MGB Biobank Portal, operational since 2015), including QC controls.

9.9.9 Security Management

Data will be stored in cloud infrastructure. To comply with the government's Cloud Smart policy, all PHI will live within a FISMA Moderate cloud environment that has received an ATO from NHLBI, which includes network firewalls and systems for access control, change control, continuous monitoring, and training. A System Security Plan, which will be reviewed and approved by NHLBI as part of the ATO, describes the cybersecurity and IT management plan in detail.

[figure not shown]
A secure, cloud-based platform called InteleShare will be used to manage images. InteleShare allows institutions to share de-identified medical images directly, without the need for physical media. All RECOVER personnel interacting with either end of the platform's upload-download workflow will be required to complete dedicated training to ensure every protection of participant information is maintained.

10 Safety and Adverse Events

10.1 Definitions

Unanticipated Problems Involving Risk to Subjects or Others

Any event, incident, experience, outcome, or new information that meets **all** of the following criteria:

- unexpected in nature, severity, or frequency given the information provided in research-related documents and characteristics of the subject population being studied; and
- is related or possibly related to participation in the research; and
- suggests that the research caused harm to subjects or others or places subjects or others at increased risk of harm (including physical, psychological, economic, or social harm) than was previously known or recognized

Please refer to 10.3 for reporting requirements.

Adverse Event

An **adverse event** (AE) is defined as any physical and psychological harm occurring to subjects during the course of participating in research, whether or not it is related to participation in the research (**excluding** symptoms, signs and co-morbidities already captured in the PASC symptom, co-morbidity, laboratory results or procedure results forms), or an adverse consequence of a study-related procedure. An AE can be any unfavorable or unintended event that is temporally related to the research.

Known manifestations of acute and post-acute SARS-CoV-2 infection will be recorded as endpoints on the PASC symptom, co-morbidity, laboratory results or procedure results forms in REDCap, rather than as AEs or SAEs, even if occurring in uninfected individuals.

Serious Adverse Event

Adverse events are classified as serious or non-serious. A serious adverse event is any AE that is:

- fatal, OR
- life-threatening, OR
- requires or prolongs hospital stay, OR
- · results in persistent or significant disability or incapacity, OR
- a congenital anomaly or birth defect, OR
- · an important medical event

Important medical events are those that may not be immediately life threatening, but are clearly of major clinical significance. They may jeopardize the participant, and may require intervention to prevent one of the other serious outcomes noted above. For example, drug overdose or abuse, a seizure that did not result in in-patient hospitalization, or intensive treatment of bronchospasm in an emergency department would typically be considered a serious adverse event.

Preexisting Condition

[figure not shown]
A preexisting condition is one that is present at the start of the study. A preexisting condition should be recorded as an adverse event if the frequency, intensity, or the character of the condition worsens during the study period and is not captured in existing RECOVER study forms as detailed above.

Post-study Adverse Event

At the last scheduled visit, the investigator should instruct each subject to report any subsequent event(s) that the subject, or the subject's personal physician, believes might reasonably be related to participation in this study. The investigator should notify the study sponsor of any death or adverse event occurring at any time after a subject has discontinued or terminated study participation that may reasonably be related to this study.

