3.1 Background Information and Relevant Literature

COVID-19 is a global pandemic currently affecting the US, yet little is known about risk factors for illness, including more severe illness and indicators of recovery. Since its nascence in China's Wuhan province in late 2019, the outbreak has evolved with startling rapidity with approximately 177 million people infected with COVID-19, resulting in at least 3.8 million deaths globally. COVID-19 positive cases are identified with COVID-19 polymerase chain reaction test or an antigen test using saliva, nasopharyngeal or bronchial samples. Fever, chills, cough, shortness of breath, fatigue, muscle aches, loss of taste and/or smell, nausea, diarrhea, and other symptoms are typical of the acute phase of the disease. COVID-19 multiorgan manifestations are now well-documented for the acute phase of the disease. Toval illness, more than 70% of those infected report a diverse array of persistent mild to severe symptoms and diseases, from fatigue and persistent loss of taste or smell to stroke, renal failure, myocarditis, neurological syndromes, COVID-associated thrombosis, and pulmonary fibrosis. Fersistent or new symptoms after COVID infection are now termed post-acute sequelae of SARS-CoV-2 (PASC). The underlying pathophysiology of persistent symptoms after COVID-19 infection is unknown but has been proposed to be attributable to viral persistence, complications from critical illness related to prolonged intubation, prolonged bed rest, and malnutrition or impacts of pandemic-related disruptions on health.

The goal of this study is to identify, evaluate, and characterize the heterogeneity in the pace and extent of recovery after acute COVID-19 infection, the clinical course of PASC symptoms in subjects who have recovered from acute infection, and the risk factors associated with the severity of the clinical course of PASC. This prospective longitudinal observational cohort study will focus on the biological differences that distinguish those who recover quickly from those who develop PASC symptoms and the long effects of COVID-19 infection, while explicitly considering racial/ethnic disparities in risks and outcomes. Data acquired from this study will provide accurate and quantifiable measures for PASC symptoms in selected case and control populations and allow for comparisons among groups to provide clues on PASC progression and complete recovery.

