Right heart cardiac catheterization: Bruising or bleeding may occur at the catheter insertion site and, in rare cases, infection or occlusion from a blood clot at the insertion site may also occur. Participants may be asked to lie down for the test in a way that could be uncomfortable or might hurt later. If occlusion does occur during the procedure, it will be addressed by draining the blood clot. If the catheter is inserted in a vein in the neck, there are very low risks of vein or artery damage, vessel perforation, internal hemorrhage,

hemothorax, cardiac tamponade, air embolism, lung collapse, heart attack or stroke, nerve injury, damage to heart valves, dizziness, low oxygen, low blood pressure (hypotension) or high blood pressure (hypertension) which may result in in-patient hospitalization. The catheterization can lead to abnormal heart rhythms. In very rare cases, therapy may be necessary. Serious changes may require treatment with emergency defibrillation (application of electrical shock to the heart). There may also be risks associated with the use of sedation or local lidocaine administration (see above). Fluoroscopy is required to ensure correct catheter placement. The effective radiation dose from fluoroscopy is approximately 1.7 mSv, about half as much as the yearly dose from natural environmental radiation in the US (3.1 mSv). There may also be risks associated with the use of electrocardiogram (see above).

Cardiopulmonary exercise testing: Complications of exercise testing are rare. Major complications of exercise testing may include abnormal heart beats (arrhythmias); change in blood pressure (for example, too high or too low); heart attack (myocardial infarction); muscle, bone, or joint injury; or death. If the test causes abnormal heartbeats (palpitations), we may need to give the participant a special medicine or treatment. Serious changes may mean the participant may need to have emergency defibrillation (giving an electrical shock to the heart). These complications happen in less than 1 in every 5,000 to 10,000 tests, with death estimated at 1 in every 20,000 tests. There may also be risks associated with the use of electrocardiogram (see above).

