10.2 Recording of Adverse Events in REDCap

At each contact with the participant, the investigator will seek information on adverse events. Information on all adverse events will be recorded immediately in the adverse event form in REDCap Central, unless the event is captured on another form in REDCap Central. Related signs, symptoms, and abnormal diagnostic procedures results should be recorded as a single event/diagnosis in REDCap Central. Note that while AEs

and SAEs should be recorded in REDCap whether related to the study or not, only related events need prompt IRB reporting (see Section 10.3).

The clinical course of each event will be followed until resolution, stabilization, or until it has been determined that the study participation is not the cause. Thus, only events that are related to study participation need to be followed until resolution or stabilization.

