11.2 Data Safety Monitoring Plan

The Data and Safety Monitoring Plan for this trial will follow recommended monitoring principles for an observational study of a vulnerable population. Oversight of data and safety is provided by the RECOVER Observational Safety Monitoring Board appointed by NHLBI. The OSMB will be composed of experts in longitudinal research (adult and pediatric populations), clinical experts in adult and pediatric manifestations of COVID-19, biostatistics, bioethics, and patient/caregiver representatives. The OSMB will also appoint ad hoc members with subspecialty expertise in the diverse array of clinical manifestations of PASC. The OSMB will meet at least twice a year to review data on AEs, adverse reactions, suspected adverse reactions, unanticipated events, patient-reported outcomes, data quality, and study recruitment, and make recommendations about study conduct to the NHLBI. As the PASC study does not involve any interventions, an early stopping rule for efficacy or futility is not indicated.

After each OSMB meeting, the OSMB determination letter and a summary report of adverse events will be prepared within 30 days and will be distributed by NHLBI staff to each principal investigator and study coordinator for review. The summary report will contain the following information:

- A statement that an OSMB review of outcome data, adverse events, and information relating to study performance across all centers took place on a given date.
- A statement as to whether or not the frequency of adverse events exceeded what was expected and indicated in the informed consent.
- A statement that a review of recent literature relevant to the research took place.
- The OSMB's recommendation with respect to progress or need for modification of the protocol or informed consent. If the OSMB recommends changes to the protocol or informed consent, the rationale for such changes and any relevant data will be provided.

• A statement that if safety concerns are identified, the NHLBI Program Official will communicate these promptly to the investigators.

12 Statistical Considerations

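### Sections 10.1 and 10.2 conflict on whether a harm caused by a study procedure goes on the AE/SAE form, so the frequency of expected procedure harms can be undercounted

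*Protocol*

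**What the plan says.** Section 10.1 of the protocol defines an adverse event in two limbs. The first covers any harm during participation, related or not, but leaves out symptoms, signs and comorbidities that the PASC symptom, comorbidity, laboratory or procedure results forms already hold. The second limb follows that exclusion: "or an adverse consequence of a study-related procedure".

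The next paragraph of 10.1 turns to known manifestations of acute and post-acute infection. These, it says, "will be recorded as endpoints on the PASC symptom, co-morbidity, laboratory results or procedure results forms in REDCap, rather than as AEs or SAEs". The rule is to hold "even if occurring in uninfected individuals". It makes no exception for an event that a study procedure caused. A serious adverse event is defined as an AE that meets a seriousness criterion, so an event that is not an AE cannot be an SAE.

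Section 10.2 requires all adverse events to be "recorded immediately in the adverse event form in REDCap Central, unless the event is captured on another form in REDCap Central".

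Section 11.2 requires the report after each board meeting to contain "A statement as to whether or not the frequency of adverse events exceeded what was expected and indicated in the informed consent". Section 10.3 separately makes two things reportable to the IRB: unexpected harm that is related or possibly related to research procedures, and new information showing that a known risk has become more frequent or more severe.

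**The concern.** This cohort performs lumbar puncture, bronchoscopy, right heart catheterization, invasive exercise testing and colonoscopy for research. A site therefore needs one clear rule for recording a harm that follows such a procedure. The protocol gives two answers and does not say which prevails. Under the second limb of the definition, a stroke after catheterization is an AE. Under the endpoint paragraph, a stroke can be entered as an outcome instead. Under 10.2, the AE form can be skipped because stroke has its own comorbidity item.

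What is at stake is the count of expected, listed harms by procedure. The 11.2 frequency statement and the 10.3 trigger for increased frequency both need that count. If sites follow the exceptions literally, both lean towards reassurance. A secondary issue is that the same events would be counted as sequelae of infection, and unevenly, because some of the procedures are done in infected participants only.

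**Working it through.** **1. Overlap of the lists.** Section 3.1 names "stroke, renal failure, myocarditis, neurological syndromes, COVID-associated thrombosis, and pulmonary fibrosis" among the conditions that follow infection. Section 4.1 lists, for catheterization through a neck vein, "hemothorax, cardiac tamponade, air embolism, lung collapse, heart attack or stroke, nerve injury". The overlap with the three-monthly items in Appendix 2 is:

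| Harm | Procedure and rate (4.1) | Appendix 2 item |
|---|---|---|
| Stroke | Right heart catheterization; very low, no figure | Stroke or bleed |
| Clot | Right heart catheterization; rare, no figure | Blood clotting problems |
| Arrhythmia | Right heart catheterization; no figure | Palpitations/arrhythmia |
| Kidney injury | Contrast CT; no figure | Kidney disease |
| Fever | Bronchoscopy; 5%, transient | Fever |
| Headache | Lumbar puncture; 3% | Headache |

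Each of the six is both a listed procedure harm and a routine form item. For each, the procedure limb of 10.1 points to the AE form, while the 10.2 waiver, and the endpoint paragraph where the event is a known manifestation, point away from it.

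**2. Whether the procedure limb settles it.** It does not. The 10.2 waiver applies to all adverse events, so an event that qualifies through the procedure limb can still be left off the AE form if another form holds it.

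**3. Whether 10.3 closes the gap.** Only in part. Its harm route is for unexpected harm, judged against risks already approved. The six harms are listed in 4.1, so at their listed nature, severity and frequency they are expected. The increased-frequency trigger would apply, but it needs the count in question.

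**4. Scale.** The inputs are from section 12.2: 12,200 infected, 2,680 uninfected, 25% of infected symptomatic, and Tier 3 shares of 68% (symptomatic infected), 3.8% (other infected) and 18.2% (uninfected).

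- The stated Tier 3 size reproduces: 0.20 × 14,880 = 2,976.
- Symptomatic infected: 0.25 × 12,200 = 3,050; Tier 3: 0.68 × 3,050 = 2,074.
- Other infected: 12,200 − 3,050 = 9,150; Tier 3: 0.038 × 9,150 ≈ 348.
- Infected in Tier 3: 2,074 + 348 ≈ 2,422. Uninfected: 0.182 × 2,680 ≈ 488.
- The sum is about 2,909, within 3% of 2,976.

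Expected events if the whole Tier 3 fraction has the test:

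- Lumbar puncture headache (infected only): 0.03 × 2,422 ≈ 73. At 25% of that uptake, about 18.
- Bronchoscopy fever: 0.05 × 2,422 ≈ 121 infected and 0.05 × 488 ≈ 24 uninfected, about 145 in all. At the 20% ceiling, 0.05 × 2,976 ≈ 149; at a quarter of the ceiling, about 37.

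**5. Effect on endpoints.** Suppose every such headache is new and is scored as a PASC symptom.

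- Headache adds 73 / 12,200 ≈ 0.6 percentage points in the infected group (0.15 at 25% uptake) and nothing in the uninfected.
- Fever adds 121 / 12,200 ≈ 0.99 points in the infected and 24 / 2,680 ≈ 0.91 in the uninfected. The difference is about 0.08 points.
- Table 7 gives 3.5 points as the minimum detectable difference for infected against uninfected in Tier 1.

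**The case against.** A reader might infer that the protocol removes any harm resembling COVID from the safety record, that such harms are lost to safety review, and that PASC estimates are materially biased. The documents do not support this.

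- The procedure limb makes procedure harms AEs, and it stands outside the form-based exclusion. The defect is a contradiction, not a clean rule of removal. The endpoint paragraph covers known manifestations, not anything that looks like one.
- Perforation, tamponade, hemothorax and pneumothorax are not among the COVID manifestations that the protocol names, so they stay AEs.
- Unexpected related harm goes to the IRB without needing an AE form entry. The board also sees unanticipated events, patient-reported outcomes and outcome data.
- The exclusion and the waiver depend on capture. AEs are recorded at once, while the symptom survey comes every 90 days. A transient fever may never reach the survey; then neither capture rule applies and no endpoint is affected.
- The event counts are ceilings. The 20% is a maximum, participants may decline, exclusions are long, and lumbar puncture oversamples people who already have headaches. Neither fever nor headache is in the PASC score listed in Appendix 5.

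All of this stands, and it limits the point to expected harms and their frequency. Two replies do not dispose of what remains. Keeping outcomes out of AE reporting is a reasonable choice in an observational study, but it does not require leaving out harms that the study's own procedures cause. The manual of operations or the SOPs, which are not shown, may give an attribution rule. Section 6.1.2 says procedure SOPs are written to be consistent with the protocol, and it is the protocol that conflicts.

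**Conclusion.** The point holds as a conflict in the recording rules. Followed literally, the endpoint paragraph of 10.1 and the waiver in 10.2 let expected procedure harms stay out of the AE/SAE count, although 10.1 itself calls procedure harms AEs. The consequence is a possible undercount, by procedure, of the harms that 11.2 and the increased-frequency trigger in 10.3 rely on. The board's other data do not replace that count, because the protocol describes no field that attributes a symptom or comorbidity to a procedure.

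Where 4.1 gives a rate, up to about 73 headaches and 145 to 149 fevers are at issue, assuming full Tier 3 uptake. For stroke, clot, arrhythmia and kidney injury no rate is given, so no number can be put on them.

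The effect on PASC endpoints is secondary and small: at most about 0.6 points for headache in infected participants, and probably less. It is unbalanced, because Appendix 5 limits lumbar puncture, muscle biopsy, right heart catheterization and invasive exercise testing to infected participants. The case for a change rests on safety counting, not on bias in the primary endpoint.

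**What to change.** Reconcile 10.1 and 10.2. State that neither the endpoint rule nor the exception for events held on another form applies to an event that the investigator judges related or possibly related to a study procedure. Such an event goes on the AE/SAE form even if it also appears on a symptom, comorbidity, laboratory or procedure results form.

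Add a procedure-related flag to those forms, so that the board can tabulate harms per procedure against the rates in 4.1 and endpoint analyses can identify the flagged events.

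The cost is about two sentences, one eCRF field and limited double entry. It needs no extra visits or participants.

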10.2 Recording of Adverse Events in REDCap

At each contact with the participant, the investigator will seek information on adverse events. Information on all adverse events will be recorded immediately in the adverse event form in REDCap Central, unless the event is captured on another form in REDCap Central. Related signs, symptoms, and abnormal diagnostic procedures results should be recorded as a single event/diagnosis in REDCap Central. Note that while AEs

and SAEs should be recorded in REDCap whether related to the study or not, only related events need prompt IRB reporting (see Section 10.3).

The clinical course of each event will be followed until resolution, stabilization, or until it has been determined that the study participation is not the cause. Thus, only events that are related to study participation need to be followed until resolution or stabilization.

10.3 Reporting New Information to the IRB

Federal regulations require timely filing of unanticipated problems posing risks to subjects or others to the local IRB. These events are:

- unexpected, AND
- · related or possibly related to study participation, AND
- serious or involve risks to subjects or others

This section also describes the NYULH IRB reporting requirements for other types of events, though investigators at participating sites are responsible for meeting any additional local requirements and/or those of the relevant sIRB. The following categories of events are considered reportable and require a submission to the IRB using the Reportable New Information e-submission form.

- 1. New or Increased Risk Information arising from the study that indicates a new or increased risk or safety issue. For example:
- New information (e.g., an interim analysis, safety monitoring report, publication in the literature, sponsor report, or investigator finding) that indicates an increase in the frequency or magnitude of a previously known risk or uncovers a new risk.
- Protocol violation that harmed subjects or others, or that indicates subjects or others might be at increased risk of harm.
- Complaint of a subject that indicates subjects or others might be at increased risk of harm or at risk of a new harm.

2. Unexpected Harm to a Subject or Other Individual

Any harm experienced by a subject or other individual(s) that, in the opinion of the investigator, is unexpected and related or possibly related to the research procedures. Harms can include psychological, economic, legal, and other non-physical harms.

[figure not shown]
- A harm is "unexpected" when its specificity or severity is inconsistent with risk information
 previously reviewed and approved by the IRB in terms of nature, severity, frequency, and
 characteristics of the study population
- A harm is "probably related" to the research procedures if, in the opinion of the investigator, the research procedures more likely than not caused the harm

Examples of harm include:

- a. Death of a Research Subject. Investigators are required to report deaths of research participants to the IRB if the death was unanticipated and related or probably related to participation in the study.
- b. Adverse Events. Only Unanticipated Adverse Events that are related to the research need to be reported to the IRB. As described above, RNI includes events that may increase risks or cause harm.

3. Non-Compliance

Non-compliance with federal regulations governing human research, NYU Langone Health's HRP policies, or with IRB requirements or determinations, or allegations of such non-compliance.

4. Audits

External audits, inspections, or inquiries by a federal agency and any resulting reports (e.g., FDA Form 483).

5. Reports

Written reports of study monitors, reports to/from a study sponsor or other information that indicates a change to the risks or potential benefits of the research.

6. Researcher Error

Failure to follow the protocol due to the action or inaction of the investigator or research staff.

7. Breach of Confidentiality

Breach of subject or patient confidentiality, data breach, or data incident. Any unauthorized disclosure of subject's personally identifiable information.

8. Unreviewed Change

Any change in the IRB-approved study protocol that was taken without prior IRB review to eliminate immediate hazard to subjects must be reported. This would include protocol violations and deviations.

A protocol violation refers to an accidental or unintentional change to the IRB-approved protocol that harmed subjects or others, or that indicates subjects or others may be at increased risk of harm. Examples: subject received the wrong dose of study medication.

9. Incarceration

Investigators must report to the IRB when a subject who is enrolled in a study that is not IRB-approved to involve prisoners becomes incarcerated and the study team plans to continue study activities with prisoners while incarcerated.

10. Complaint

Complaints made by a subject that are related to the study and either indicate increased risk and/or that cannot be resolved by the research team must be reported.

11. Suspension or Termination

Principal Investigators must report premature suspension or termination of the research by the sponsor, investigator, or institution.

[figure not shown]
When to Report Events

Report promptly, but no later than 5 calendar days from the time the investigator becomes aware of the event:

- Unanticipated Problems Involving Risk to Subjects or Others (see Section 10.1 for definition), if
 the event requires immediate intervention to prevent serious harm to subjects or others, or the
 subject suffered serious harm.
- Death of a Participant, if it is unexpected and related to a study procedure

For all other reportable events listed above, report promptly, but no later than 10 calendar days from the time the investigator becomes aware of the event:

The IRB will accept other reports when the Principal Investigator is unsure whether the event should be reported. The Principal Investigator should first contact IRB Operations by email or telephone to determine if the reporting is necessary under this Policy.

Events that do not meet the above criteria for immediate reporting should be summarized and reported to the IRB at the time of continuing review.

Reporting Process

The reportable events noted above will be reported to the IRB using a Reportable New Information submission and will include a description of the event with information regarding reporting category above, follow-up/resolution, and need for revision to consent form and/or other study documentation. Copies of each report and documentation of IRB notification and receipt will be kept in the Clinical Investigator's study file.

